5.6.3 Deaths

5.6.3.1 Presentation

A summary of deaths will be provided with the number and percentage of participants categorised as:

- Related to disease under investigation only
- AE outcome = death only
- Both related to disease under investigation and with AE outcome = death
- AE with outcome = death > 30 days after last study intervention
- Other deaths

A corresponding listing will also be produced.

5.6.4 Clinical Laboratory, Blood Sample

5.6.4.1 Definitions and Derivations

Laboratory tests will be grouped according to chemistry, haematology and coagulation. Listings will be provided for all laboratory results. Laboratory parameters will be assessed at baseline as well as throughout the study.

For chemistry and haematology parameters, laboratory abnormalities with toxicity grades according to the NCI CTCAE version 5.0 will be derived.

Laboratory variables that will be measured are detailed in

Table 8 Laboratory Safety Variables

.

Table 8 Laboratory Safety Variables

Haematology/Haemostasis (whole blood)		Clinical Chemistry (serum or plasma)	
B-Full blood count with differential		S/P-Creatinine	S/P-Chloride
B-Hb		S/P-Bilirubin total	S/P-Magnesium
B-White blood cell count with differential		S/P-Direct and indirect bilirubin (where required)	S/P-Phosphorus
B-Platelet count		S/P-Alkaline phosphatase	S/P-Cholesterol
B-Haemocrit		S/P-Aspartate transaminase	S/P-Amylase
B-Absolute neutrophil count		S/P-Alanine transaminase	S/P-Lactate dehydrogenase
B-Absolute lymphocyte count		S/P-Albumin	S/P-Lipase
B-Blast Cells		S/P-Potassium	S/P-Bicarbonate
Urinalysis (dipstick)		S/P-Carbonate	S/P-glutamate dehydrogenase
U-Hb/Erythrocytes/Blood	U-pH	S/P-Calcium, total	S/P-Blood urea nitrogen
U-Protein/Albumin	U-Bilirubin	S/P-Sodium	S/P-Glucose (fasting preferred)
U-Glucose	U-Ketones	S/P-Creatine phosphokinase	S/P-Total protein
U-Specific gravity	U-Drug screening ^a	S/P-Uric acid	S/P-GGT
U-Microscopy including white blood cells /high-power field, red blood cells/high-power field		S/P-Triglycerides	S/P-Ferritin
Coagulation		S/P-C-reactive protein	S/P-Urea
International normalised ratio		S/P-Troponin	S/P-Phosphate
Activated partial thromboplastin time, absolute or relative		S/P-Ammonia (where available at local institution; to be tested every 2 weeks)	
Prothrombin time			
Fibrinogen			
D-Dimer (where available at local institution)			
Pregnancy Test (women of childbearing potential only)			
U-hCG		S-beta hCG (at screening only)	

^a Mandated at screening visit only; for all other urinalysis tests, drug screening may be performed at investigator discretion.

Abbreviations: B, blood; GGT, gamma-glutamyl transferase; Hb, haemoglobin; hCG, human chorionic gonadotropin; P, plasma; S, serum; U, urinalysis.

Change from baseline in haematology, clinical chemistry and coagulation endpoints will be calculated for each post-baseline timepoint. CTCAE grade is calculated at each timepoint for

tests with CTCAE grading defined. Maximum on-treatment CTCAE will be also calculated. Absolute values will be compared to the local laboratory reference range and classified as low (below range), normal (within range or on limits of range) and high (above range). All values classified as high or low will be flagged on the listings.

Liver Function Parameters

Participants with elevated post-baseline ALT, AST, or Total Bilirubin will be identified.

5.6.4.2 Presentations

The absolute values and change in each laboratory parameter from baseline to each post-baseline timepoint will be summarised graphically in box plots.

Laboratory abnormalities occurring during the on-treatment period to the last assessment on treatment will be presented. Worst toxicity grade, rates of grade 3-4 toxicity, and grade shifts of 2 or more from baseline to the maximum grade will be presented. Summaries indicating hyper- and hypo- directionality of change will be produced, where appropriate. Laboratory parameters that cannot be graded via NCI CTCAE will be summarised with frequencies of post-baseline laboratory values categorized as low (L), normal (N), or high (H) using laboratory normal ranges compared to baseline.

Listings will be provided for all laboratory results.

Liver Function Parameters

Number and percentage of participants with elevated post-baseline ALT, AST, or Total Bilirubin will be tabulated.

For participants with “Potential Hy’s law”, the change in the following laboratory parameters from baseline to each post-baseline timepoint will be summarised: ALT, AST, alkaline phosphatase, glutamate dehydrogenase, lactate dehydrogenase, gamma-glutamyl transferase, and international normalised ratio. Individual participant data for these laboratory parameters will be listed as well.

Plots for both maximum on-treatment ALT and AST versus the maximum on-treatment bilirubin (expressed as multiples of their upper limit of normal [ULN] reference range) will be produced, with reference lines at 3 x ULN for ALT and AST and 2 x ULN for total bilirubin.

Liver biochemistry test results over time for participants with elevated ALT or AST (≥ 3 x ULN) and elevated bilirubin (≥ 2 x ULN) regardless of whether or not these elevations coincide, or ALT or AST ≥ 5 x ULN will be plotted.

5.6.5 Clinical Laboratory, Urinalysis

5.6.5.1 Definitions and Derivations

Urinalysis variables that will be measured are detailed in

Table 8 Laboratory Safety Variables

5.6.5.2 Presentations

Shift tables (“Negative”, “Trace”, “Positive”, “0”, “+”, “++”, “+++”) from baseline to worst on-treatment results will be produced for urinalysis.

Listings will be provided for all laboratory results including urinalysis.

5.6.6 Vital Signs

5.6.6.1 Definitions and Derivations

Temperature, blood pressure and heart rate will be assessed.

5.6.6.2 Presentations

Vital signs will be assessed at baseline and throughout the study. Vital signs will be summarised by study timepoint including descriptive statistics for the value of the parameters and the changes from baseline.

Absolute values and change from baseline for vital signs data at each timepoint will be presented using box plots.

5.6.7 Weight

5.6.7.1 Presentations

Weight will be assessed at baseline and throughout the study. Weight will be summarised by study timepoint including descriptive statistics for the value and changes from baseline.

Absolute values and change from baseline for weight at each timepoint will be presented using box plots.

5.6.8 B symptoms

5.6.8.1 Presentations

Information on B symptoms (unintentional weight loss, disease related intermittent fevers >38 C, drenching sweats especially at night, significant fatigue, worsening of B-symptoms compared to baseline, worsening of B-symptoms compared to prior timepoint, and comments) will be listed for all subjects and timepoints.

5.6.9 Tumour lysis syndrome

5.6.9.1 Definitions and Derivations

Tumour lysis syndrome (TLS) is an important identified risk for AZD4573. TLS prophylaxis is mandatory for all participants starting 3 days before the first dose of AZD4573, which should be followed in addition to institutional guidelines.

There are 2 data sources to report TLS: AEs of TLS and TLS monitoring data. One TLS AE per infusion per participant will be counted. For participants with multiple TLS AEs recorded after one infusion, only the TLS AE with maximum CTCAE grade will be counted for reporting purposes. Similar rules apply to TLS monitoring data. According to the TLS monitoring schedule in the CSP, participants could have multiple TLS monitoring episodes after one infusion, if counting TLS monitoring assessments at each unique date and time per participant as an episode. For reporting purposes, a maximum of one TLS per infusion per participant will be counted. The highest Cairo-Bishop grade of each clinical characteristic (creatinine abnormality, cardiac arrhythmia, seizure) and overall grading will be computed for each infusion and participant.

Overall Cairo-Bishop grading for Clinical TLS is defined as the maximum overall on treatment Cairo-Bishop grading, derived from the highest contributing grade (creatinine abnormality, cardiac arrhythmia, seizure) for a specific episode of clinical TLS.

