8.3.2 Follow-up of AEs and SAEs

Any AEs that are unresolved at the participant's last assessment in the study are followed up by the investigator for as long as medically indicated, but without further recording in the eCRF. AstraZeneca retains the right to request additional information for any participant with ongoing AE(s)/SAE(s) at the end of the study, if judged necessary.

After the initial AE/SAE report, the Investigator is required to proactively follow each participant at subsequent visits/contacts. All SAEs and non-serious AEs will be followed until resolution, stabilisation, the event is otherwise explained, or the participant is lost to follow-up.

Adverse event variables

The following variables will be collected for each AE:

- AE (verbatim)
 - The capture of diagnoses is preferred over all associated signs and symptoms. For example: laboratory TLS, clinical TLS, cytokine release syndrome. Provisional diagnoses (eg, PHL) must be updated as soon as possible.
- The date when the AE started and stopped
 - When the onset of an AE in relation to dosing is rapid, for example TLS, it is important to record the **exact time of the start of infusion** dosing and the **time of AE onset** in addition to the dates.
- CTCAE grade/changes in CTCAE grade
- **For TLS events:** Adverse events of TLS shall be graded according to CTCAE. The AE verbatim shall discriminate between laboratory and clinical TLS. In addition, TLS events will be graded according to Howard modification of the Cairo-Bishop grading system (see [Appendix G](#)) on the TLS monitoring eCRF form.
- Whether the AE is serious or not

- Investigator causality rating against the IP(s) (yes or no)
- Action taken with IP(s) in response to the AE (for example: no action, dose reduced, treatment temporarily stopped, treatment permanently discontinued).
- Outcome of the event

In addition, the following variables will be collected for SAEs:

- Date AE met criteria for SAE
 - The date of start of first signs and symptoms should be captured together with the date the event became serious.
- Date investigator became aware of SAE
- Reason AE is classified as serious
- Date of hospitalisation
- Date of discharge
- Probable cause of death
- Date of death
- Autopsy performed (yes/no)
- Causality assessment in relation to Study procedure(s)
- Causality assessment to other medication

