10.6.2.1.2 TLS Monitoring and Management

Please refer to [Appendix G](#) for the definition of TLS and the TLS grading criteria to be used in this study.

All participants will receive TLS prophylaxis during the intra-participant dose ramp-up and be monitored for TLS during the first 24 hours post start of infusion during the intra-participant dose ramp-up (see Sections [10.6.2.1.1](#) and [10.6.2.1.2](#)). If there are no signs of TLS at the 6 hour TLS monitoring assessment, the participant can be managed as an outpatient at the discretion of the investigator and return to the clinic the next day to complete the 24 hour TLS monitoring assessment. Participants showing signs of TLS at 6 hours after the start of infusion must remain admitted for inpatient TLS monitoring approximately every 6 hours (or more frequently if clinically indicated) until the 24 hour TLS monitoring assessment.

Where hospitalisation for longer than the mandated 24 hours is required it should be noted that if this is due to occurrence of an AE then the event must be reported as an SAE, per definition. However, if it is purely for the purposes of extended observation then this does not qualify as an SAE and does not need to be reported.

For all participants, results of safety laboratory testing (haematology and clinical chemistry at a minimum) must be available within 72 hours prior to dosing and must be reviewed by the investigator prior to each administration of AZD4573. For each TLS monitoring timepoint, a TLS Monitoring page in the eCRF is to be filled out.

In particular, the uric acid level must be < ULN prior to the start of each AZD4573 infusion.

It is strongly recommended that for all participants with elevated uric acid (hyperuricaemia) and intermediate/high risk of TLS, prophylaxis should be administered prior to AZD4573 per Section 10.6.2.1.1 and repeated as clinically indicated thereafter as per local standard.

Monitoring for TLS includes checking potassium, calcium, phosphate, uric acid, and creatinine. Fluid balance must be monitored according to institutional standards.

Any participant developing laboratory TLS must be treated promptly for electrolyte abnormalities (such as hyperkalaemia) to prevent arrhythmias/seizures and for elevated uric acid (hyperuricaemia) with rasburicase (0.20 mg/kg/d IV over 30 minutes for up to 5 days) to prevent acute renal failure and monitored closely for signs of progression to clinical TLS.

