NCI	National Cancer Institute
NK	natural killer
NKTCL	natural killer/T-cell lymphoma
OAE	other significant adverse event
ORR	overall response rate
OS	overall survival
CCI	CCI
CCI	CCI
PCR	polymerase chain reaction
PD	progressive disease
PET	positron emission tomography
PFS	progression free survival
PHL	potential Hy's Law
PK	pharmacokinetic
PK/PD	pharmacokinetic/pharmacodynamic
PR	partial response
PTCL	peripheral T-cell lymphoma
RECIST	Response Evaluation Criteria in Solid Tumors
RP2D	recommended phase II dose
r/r	relapsed/refractory
SAE	serious adverse event
SAP	Statistical Analysis Plan
SCT	stem cell transplantation
SD	stable disease
SoA	schedule of activities
SoC	standard of care
SOI	start of infusion

Abbreviation or special term	Explanation
SRC	Safety Review Committee
SUSAR	suspected unexpected serious adverse reaction
TBL	total bilirubin
TEAE	treatment emergent adverse event
TLS	tumour lysis syndrome
TPV	third-party vendor
TSH	thyroid stimulating hormone
ULN	upper limit of normal
US	United States
WOCBP	women of childbearing potential

Appendix G Cairo-Bishop Tumour Lysis Syndrome Definition and Grading Criteria (Howard Modification)

Laboratory tumour lysis syndrome (TLS) is defined as a level above or below normal, as defined below, for any 2 or more serum values of uric acid, potassium, phosphate, and calcium within 3 day before or 7 day after the initiation of anti-cancer therapy. This assessment assumes that a participant has or will receive adequate hydration and a hypouricaemic agent(s).

Cairo-Bishop Definition of Laboratory Tumour Lysis Syndrome (Howard Modification)

Element	Value
Uric Acid	$\geq 476 \mu\text{mol/L}$ (8 mg/dL)
Potassium	$\geq 6.0 \text{ mmol/L}$ (6 mg/L)
Inorganic phosphorus	$\geq 1.45 \text{ mmol/L}$ (4.5 mg/dL)
Calcium	$\leq 1.75 \text{ mmol/L}$ (7.0 mg/dL)

[Howard et al 2011](#)

Cairo-Bishop Definition of Clinical Tumour Lysis Syndrome

Clinical tumour lysis syndrome assumes the laboratory evidence of metabolic changes and significant clinical toxicity that requires clinical intervention. Clinical tumour lysis syndrome is defined as the presence of laboratory tumour lysis syndrome and any 1 or more of the below-mentioned criteria. Maximal clinical tumour lysis syndrome manifestation (renal, cardiac, neuro) defines the grade.

- (1) Creatinine $\geq 1.5 \times \text{ULN}$ (age > 12 years or age adjusted)
- (2) Cardiac arrhythmia/sudden death
- (3) Seizure

Cairo-Bishop Clinical Tumour Lysis Syndrome Grading Criteria

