5.6.9.2 Presentations

The number and percentage of participants with AE LLTs involving clinical TLS and laboratory TLS by maximum CTCAE grade will be presented, including the total number of AEs. Figures for laboratory TLS and clinical TLS will be presented. Bar charts showing the number of TLS AEs and the number and percentage of participants having TLS AEs by week since AZD4573 administration will be presented. TLS-associated AEs will be listed with other AEs.

Time from infusion to onset of TLS after first AZD4573 administration and after subsequent doses will be summarised using TLS monitoring data. Listing of TLS monitoring will be presented including uric acid, potassium, phosphate, calcium, urea nitrogen, creatinine, creatinine elevation due to TLS, cardiac arrhythmia due to TLS, seizure due to TLS and Cairo-Bishop grades for clinical TLS.

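### SAP 5.6.9 keeps one TLS adverse event per infusion across both types and then reports laboratory and clinical TLS separately, so one type can drop out of its own row

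*SAP*

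**What the plan says.** SAP 5.6.9.1 sets the counting unit for TLS adverse events: "One TLS AE per infusion per participant will be counted". If more than one is recorded after an infusion, "only the TLS AE with maximum CTCAE grade will be counted for reporting purposes". Neither sentence mentions type, and no rule covers equal grades. The TLS monitoring data are limited in a similar way: "For reporting purposes, a maximum of one TLS per infusion per participant will be counted".

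SAP 5.6.9.2 then reports by type. "The number and percentage of participants with AE LLTs involving clinical TLS and laboratory TLS by maximum CTCAE grade will be presented", together with the total number of AEs. It adds: "Figures for laboratory TLS and clinical TLS will be presented". It does not say whether those figures draw on the AE data or the monitoring data. All TLS-associated AEs also go into the AE listing.

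The protocol keeps the two types apart at the point of recording. Section 8.3.2 states: "The AE verbatim shall discriminate between laboratory and clinical TLS". Appendix G nests one in the other: "Clinical tumour lysis syndrome is defined as the presence of laboratory tumour lysis syndrome and any 1 or more of the below-mentioned criteria". Section 10.6.2.1.2 expects that one can lead to the other, since a participant with laboratory TLS is to be "monitored closely for signs of progression to clinical TLS".

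**The concern.** The rule selects one event across both types, and the output splits the selected events by type. Any infusion followed by a laboratory and a clinical TLS record therefore contributes to only one of the two rows, and CTCAE grade decides which. A reader of the table would take the laboratory row to mean everyone with a laboratory TLS event and the clinical row to mean everyone with a clinical one. Under the rule, neither is guaranteed.

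TLS is an important identified risk and an adverse event of special interest for this drug, and cohorts are planned at about 21 response-evaluable participants, so one lost participant is visible in a percentage. The missing tie-break adds a reproducibility problem: two programmers following the SAP could produce different tables from the same data.

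**Working it through.** The documents give no TLS rate or count, so there is no plan figure to reproduce. The check applies the SAP rule to small constructed records and compares it with the same rule applied within each type.

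**Rules compared**
- SAP rule: for each participant and infusion, keep the single TLS AE with the highest CTCAE grade.
- By-type rule: for each participant, infusion and TLS type, keep the single AE with the highest CTCAE grade.

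**Records**
- A: laboratory grade 3 and clinical grade 4 after one infusion.
- B: as A, plus laboratory grade 3 after a second infusion.
- C: laboratory grade 3 and clinical grade 3 after one infusion.

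**Results, as events (participants)**

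| Case | Laboratory, SAP rule | Laboratory, by type | Clinical, SAP rule | Clinical, by type | Participants with any TLS, either rule |
|---|---|---|---|---|---|
| A | 0 (0) | 1 (1) | 1 (1) | 1 (1) | 1 |
| B | 1 (1) | 2 (1) | 1 (1) | 1 (1) | 1 |
| C, laboratory record read first | 1 (1) | 1 (1) | 0 (0) | 1 (1) | 1 |
| C, clinical record read first | 0 (0) | 1 (1) | 1 (1) | 1 (1) | 1 |

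- In A the laboratory row loses both the event and the participant.
- In B the laboratory row loses an event but keeps the participant, because the second infusion also counts. Had that second event been grade 2, the participant would appear in the laboratory row at grade 2 instead of grade 3.
- In C the outcome depends on record order, and one of the two orders removes the clinical event.
- The number of participants with any TLS is 1 throughout.

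**Size per participant lost.** One participant missing from a row lowers its incidence by 100 × 1/N percentage points. N is an assumption: it takes the safety set to be about the planned size.
- N = 21 (one cohort): 100/21 = 4.8
- N = 30 (planned maximum for cHL): 100/30 = 3.3
- N = 63 (three cohorts of 21): 100/63 = 1.6
- N = 90 (approximate planned maximum for Module 1): 100/90 = 1.1

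**The case against.** The strongest reply is that two records may seldom exist. Protocol 8.3.5 says that when a laboratory deterioration comes with clinical signs, the sign or symptom is the AE and the laboratory result is supporting information; it also prefers the clinical term. Section 8.3.2 prefers a diagnosis and collects grade changes within an AE. An episode that progresses could then be one record, and nothing would be dropped. This stands as a limit on frequency. It does not remove the problem, because SAP 5.6.9.1 itself provides for several TLS AEs after one infusion and does not restrict them to one type.

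A second reply is that the SAP does not state the order of operations, so the rule might be meant to apply within each type. That reading would allow two TLS AEs to count after one infusion, which "One TLS AE per infusion per participant will be counted" excludes. At best the text is ambiguous.

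A third is that the sponsor may intend clinical TLS to absorb laboratory TLS. That would be reasonable, but the rule selects on grade, so it fails to do this at ties and whenever the laboratory record is graded higher.

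A fourth is that the information survives elsewhere. The listings keep every TLS AE, and the monitoring data give a Cairo-Bishop grade per infusion that does not depend on choosing between AE records. TLS is also summarised as an AESI in SAP 5.6.2.2, where no one-per-infusion rule is stated. This is true and lowers the stakes. But those outputs do not correct an AE table by type, and the AESI summaries are grouped by preferred term rather than specified at the lower level that carries the split.

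Some stronger readings are tempting and not supported:
- A reader might infer that clinical TLS is the count most at risk because it occurs in the worst cases. A maximum-grade rule keeps the more severe record; clinical TLS is lost only at a tie or when laboratory TLS is graded higher, and the documents give no frequency for either.
- A reader might infer that TLS incidence overall is understated. Participants with any TLS are counted correctly.
- A reader might infer that safety oversight is impaired. The TLS criterion for pausing recruitment in protocol 7.1.1 rests on assessment of individual events, not on this table.

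**Conclusion.** SAP 5.6.9.1 and 5.6.9.2 do not fit together as written. If laboratory and clinical TLS are recorded as separate AEs after one infusion, the lower-graded type is removed from its own row; at equal grades the SAP leaves the choice undefined, and clinical TLS can be the one removed. The event count for the dropped type is always too low in that situation. The participant count is too low only if that type is not counted after another infusion in the same participant.

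The conclusion rests on two conditions: that separate records exist, and that the rule is applied as worded, across types. The total effect cannot be computed, because the documents do not give the frequency of co-recording or of ties. It could be nil. The point is minor: a descriptive safety table in a single-arm module, with full listings behind it.

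**What to change.** Add to SAP 5.6.9.1 that, for tables and figures by type, the maximum-grade rule applies within each type, giving at most one laboratory and one clinical TLS AE per participant and infusion. For the combined TLS count, keep one event per infusion and retain the clinical event when both are present, so that one evolving episode is not counted twice. State which grade the combined row shows if the laboratory record was graded higher. In 5.6.9.2, name the data source for the figures by type.

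An acceptable alternative is to declare that clinical TLS takes precedence, select on type before grade, and label the other row as laboratory TLS only.

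The cost is about one sentence in the SAP and a small programming change, with no new data collection. The downside of the main option is that the two type-specific counts may sum to more than the combined count; a table footnote can say so.
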